All (serious) adverse events or (serious) adverse device effects will be documented on the appropriate “Adverse event/Adverse device effect form.” Safety parameters of this clinical trial are predominantly based on the documentation of adverse events, serious or non-serious, as well as expected and unexpected reactions. Also, near incidents will be reported.

SUBJECT POPULATION AND SAMPLE SIZE

Subjects in the study will be recruited within the UNC School of Dentistry Predoctoral and Graduate clinics. Up to 50 adult subjects (18 years of age and older) will be recruited to provide at least 50 sets of matched or unmatched paired teeth in need of study restorations. Fifty restorations available at baseline and 40 at the 18-month follow-up visit are the minimum number recommended in the 2001 ADA guidelines for clinical trials on resin-based composite resins for posterior restorations. Subjects will be in need of two or four medium-sized Class II restorations in molar and/or premolar teeth.

INCLUSION AND EXCLUSION CRITERIA

To be included in the study, a potential subject must satisfy the criteria described below and be available for the various follow-up visits. A record will be maintained of the reasons for the loss of subjects from the study.

Inclusion Criteria

To be considered for inclusion in the study, subjects must:

- Be older than 18 years of age.
- Have a pair of similar lesions or failed restorations in vital permanent molar or premolar teeth requiring Class II restorations of moderate size that extend between one-quarter and one-third of the way up one or more of the cuspal slopes. Any Class II restoration must have a proximal portion with at least one margin that obviously extends into an interproximal embrasure. (Note: A tooth will be considered vital for the purposes of the study if it is clinically and/or radiographically free of any signs and symptoms of periapical pathology and responds to routine vitality testing.)
- Be capable of giving written informed consent.

Exclusion Criteria

Subjects will be excluded from participating in the study if they:

- Have a history of any adverse reaction to clinical materials of the types to be evaluated.
- Have a medical or dental history that could possibly complicate the provision of the proposed restorations and/or influence the behavior and performance of the restorations in clinical service.
- Have advanced periodontitis affecting the mobility of the teeth.

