The pre-operative status and a periapical radiograph (where clinically indicated) of each tooth to be included in the study will be evaluated and a pre-treatment status form will be completed (Patient Registration Form). The condition of the gingival tissue adjacent to each tooth to be restored will be assessed (four sites: facial, lingual, mesial and distal) and recorded as pre-treatment measurements (Patient Registration Form). Oral hygiene status including plaque index will be determined after periodontal evaluation. Appropriate vitality and radiographic assessments will be completed where indicated clinically, and will be recorded. A pre-operative photographic record will be made.

The restorative material to be used will be allocated by means of a randomization scheme based on computer generated random numbers (Appendix 1). Before starting the study, the PI will decide, by means of a toss of a coin, whether even or odd numbers indicate the test or control treatment. For each set of paired teeth, the lowest numbered tooth (Universal Numbering System) will be selected first. Before cavity preparation, the first randomization number in the sequence will be noted and the allocated treatment procedure carried out as indicated by the random number obtained. The second cavity is then prepared and restored using the second treatment option (next number in the row). Restorative treatments will be randomly assigned to the study teeth at the same visit at which pre-treatment gingival condition, vitality, etc., are determined.

The treating clinician will complete the preparation and placement of restorations, and the arrangements for the subsequent follow-up of the patients.

OPERATIVE PROCEDURES

Local anesthesia will be administered unless declined by the patient. The teeth to be restored will be prepared using conventional instruments and techniques, and no bevels will be placed on any of the cavosurface margins. Shades will be selected before the procedure is started and the tooth is still moist. Rubber dam will be used.

A sectional metal matrix (Garrison Dental or similar) and bitine ring will be placed along with plastic or wooden wedges. At the operator's discretion (e.g., if the preparation is

too wide for a sectional matrix), a thin circumferential metal matrix (Convexi-T, Clinician's Choice or similar) may be used. The bonding system will be used in the selective etch mode according to manufacturer's instructions.

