Restoration placement will be completed in accordance with the recommended procedure for the materials under investigation and in a standardized fashion. After application of the adhesive, a bulk increment (up to 5 mm in thickness) of Filtek™ Bulk Fill Posterior Restorative will be placed and adapted with suitable instruments. Additional increments will be placed as needed. Filtek™ Supreme Ultra Universal Restorative will be incrementally placed in layers (no thicker than 2 mm). The composite resin (each increment of Filtek™ Supreme Ultra Universal Restorative) will be light cured following the recommended exposure time using a device provided by the sponsor. Additional light curing will be performed from facial and lingual for Filtek™ Bulk Fill Posterior Restorative after matrix removal per instructions for use.

Excess material will be removed with suitable instrumentation. Occlusion will be checked and adjusted as needed. Restorations will be polished with diamond abrasives, flexible polishing discs and finishing strips with progressively decreasing grit size (e.g. Sof-Lex™, 3M ESPE), ultra-fine grain diamonds, and/or silicone polishers at the clinicians' discretion. Impressions of restorations using the 3M True Definition Scanner and Imprint™ 3 VPS Impression Material will be taken at each follow-up visit for evaluation of wear over time. Models will be poured and wear determined using the Leinfelder method [18]. The models will also be assessed for wear via optical profiling at the Minnesota Dental Research Center for Biomaterials and Biomechanics. Digital impressions of the restored teeth will be taken at each follow-up visit using the 3M True Definition Scanner. The digital data will be analyzed for wear at 3M ESPE.

The placements and baseline assessments will be completed within 6-12 months of the agreed starting date of the evaluation.

FOLLOW-UP ASSESSMENT

During the follow-up investigation, two examiners will evaluate the restorations relative to the criteria provided by Hickel. The two examiners who undertake the reviews will work independently and will be masked to the treatment conditions. In the event of disagreement between the examiners, agreement will be reached based on discussion. The final result will be marked on the Case Report Form.

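### The material can be known to the treating clinician while both cavities of every pair are cut; disclosing the allocation after preparation would remove an avoidable, unquantified opportunity for bias

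*Combined protocol and SAP*

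**What the plan says.** The order of steps is set out under PRE-OPERATIVE PROCEDURES.

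- Code: "the PI will decide, by means of a toss of a coin, whether even or odd numbers indicate the test or control treatment". This is settled before the study starts, so a number in view identifies a material.
- First tooth (the lower-numbered of the pair): "Before cavity preparation, the first randomization number in the sequence will be noted and the allocated treatment procedure carried out".
- Second tooth: "The second cavity is then prepared and restored using the second treatment option". A parenthesis adds that this is the next number in the row of the Appendix 1 table.
- Operator: "The treating clinician will complete the preparation and placement of restorations".

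Two passages bear on the shape of the cavity. OPERATIVE PROCEDURES says: "The teeth to be restored will be prepared using conventional instruments and techniques, and no bevels will be placed on any of the cavosurface margins". The Inclusion Criteria limit lesions to "moderate size that extend between one-quarter and one-third of the way up one or more of the cuspal slopes". Neither sets a target depth or width for the finished preparation.

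Masking appears only under FOLLOW-UP ASSESSMENT, for the two examiners. The text names no separate holder of the list or code and does not withhold the material until cutting is complete.

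**The concern.** Randomization balances the lesions as they stand before treatment. It does not balance choices made after the material is known, and the finished cavity is one of those choices. If depth or extension came to differ by material, a difference in outcome would mix the effect of the material with that of the preparation.

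The protocol itself links cavity size to outcome. The INTRODUCTION says that stress in the tooth rises with restoration size, while stress within the restoration and at the adhesive interface tends to fall as the cavity gets larger. It also names marginal gaps, sensitivity and enamel microcracks among the effects of shrinkage. Table 1 scores fracture, marginal adaptation, sensitivity and tooth integrity, all within the primary endpoint. The stated hypothesis is similar performance, so an imbalance in cavities could hide a real difference as well as create a false one.

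The operator cannot be masked while placing the material. Nothing in the protocol requires the operator to know it while cutting.

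**Working it through.** The protocol gives no figure to reproduce here. The check is of the order of steps, the number of preparations affected, and what else in the text limits the problem.

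**1. Order of steps.** First number noted → first cavity cut and filled → second cavity cut and filled with the other material. The code is fixed beforehand, so noting the first number identifies the first material, and the second follows by elimination. No other section reverses this order.

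**2. Does Appendix 1 agree?** The table has 39 rows of 8 numbers. Read across in adjacent twos, that is 39 × 4 = 156 pairs. Of these, 150 hold one odd and one even number, and 6 hold two of the same parity. The first same-parity pair is the 73rd. All of the first 50 pairs are odd/even, and 25 of them begin with an even number. For the planned 50 pairs, therefore, the rule of taking the other option and the rule of taking the next number give the same answer, and the first number settles both teeth.

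**3. Preparations exposed as written.** 50 pairs × 2 teeth = 100, all of which can be cut with the material known.

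**4. Preparations blind after the change.** Let k be the number of pairs in which both teeth are prepared before either is filled. If the list is held away from the operator, the number blind is 50 + k:

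| k | Blind | Not blind |
|---|---|---|
| 0 | 50 | 50 |
| 25 | 75 | 25 |
| 50 | 100 | 0 |

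The documents do not give k, so these values only show the range. The upper end is not realistic: the current text describes the teeth one after the other, and the example pair under Distribution of restorations (#15 and #31) lies in opposite arches on opposite sides.

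**5. What the existing safeguards cover.**

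| Safeguard | Section | Protects finished depth and extension? |
|---|---|---|
| Masked examiners | FOLLOW-UP ASSESSMENT | No; protects scoring |
| Moderate lesion size, similar within the pair | Inclusion Criteria | Partly; bounds extension up the cusps, not depth |
| Conventional technique, no bevels | OPERATIVE PROCEDURES | Partly; no dimensions set |
| Chi-square, McNemar, Mann-Whitney tests | Statistical analyses | No; no adjustment for cavity size is described |

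The text describes no record of finished cavity dimensions, so an imbalance could not be examined afterwards from what is planned.

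**The case against.** The strongest reply is that the text gives the operator no motive to cut differently. A reader might infer one from the thickness figures: the test material goes in bulk up to 5 mm, while the control "will be incrementally placed in layers (no thicker than 2 mm". Under OPERATIVE PROCEDURES, however, these limits apply to each increment and not to the cavity. Further increments of the test material are allowed and the number of control layers is not capped, so either material can fill any depth. A reader might also infer that the matrix would follow the material, but the protocol ties that choice to the width of the preparation. Both objections stand, and neither inference should be used.

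Three further points are fair. The sentence on noting the number is passive and names no reader, so it does not require the operator to read it. That the operator knows is an inference, though a strong one, because the same clinician carries out the allocated procedure. Lesion size, similarity within pairs and standard technique narrow how far a cavity can be varied. And the count of 100 measures exposure, not bias.

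A last objection concerns the remedy. Changing when the number is read achieves little if the operator holds the printed table and knows the code. This is right, and it is why the fix needs a separate holder.

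None of this changes the order of steps. The safeguards limit latitude without removing it, and the knowledge during cutting serves no purpose stated in the protocol.

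**Conclusion.** The point holds as an avoidable opportunity for bias. As written, the treating clinician can know the material during all 100 planned preparations, and finished depth and extension are only partly constrained. Neither the size nor the direction of any resulting bias can be computed. The INTRODUCTION describes stresses that move in opposite directions with size, so it does not supply a direction either.

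A reader might go further and conclude that cavities will differ by material, or that later disclosure would blind every preparation. The documents support neither. They show opportunity, not occurrence, and pairs treated in sequence leave the second tooth unblinded.

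The conclusion rests on two assumptions: that the clinician learns the number when it is noted, and that 50 pairs are placed as planned. It is worth acting on because the change is cheap and a cavity cannot be re-cut blind once it has been filled. It does not call the randomized comparison as a whole into question.

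**What to change.** Under PRE-OPERATIVE PROCEDURES, replace the sentence on noting the number with wording to this effect:

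> The randomization number is disclosed to the operator only when preparation of the lower-numbered tooth is complete or, where both teeth of the pair are prepared before either is filled, when both preparations are complete. Until then a team member other than the operator, such as the chairside assistant, holds the Appendix 1 list and the odd/even code.

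Add one tick box per tooth to the case report form: prepared before disclosure, yes or no. The later sentence that treatments are assigned at the visit where pre-treatment status is determined can stay, provided it is made clear that assignment is not disclosure.

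The tick box documents how far blinding was achieved. It should not lead to an analysis restricted to blind-prepared teeth where that would keep one tooth of a pair and break the pairing. No rule on matrix choice is needed, and the number of pairs does not change.

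Costs: the material is set out after preparation instead of before, and pairs treated one after the other gain blinding for the first tooth only. Shades are chosen before the procedure starts, so the site must settle how that step works while the material is undisclosed. No extra staff or visits are needed.

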The hypothesis is that Filtek™ Bulk Fill Posterior Restorative composite resin, when used to restore posterior teeth, will exhibit similar clinical performance – in terms of wear resistance, marginal integrity, durability, and other clinical characteristics – to Filtek™ Supreme Ultra Universal Restorative composite resin, a restorative material in everyday use in dentistry.

STUDY OBJECTIVES

The purpose of this study is to compare the clinical performance of Filtek™ Bulk Fill Posterior Restorative with a commercially available conventional composite resin restorative material when used to restore Class II preparations in molar and premolar teeth.

STUDY DESIGN

The study design is a randomized, controlled, comparative effectiveness clinical trial investigation of the test materials used to restore moderate-sized Class II cavities in posterior permanent teeth in adult dental patients. The study will be of five years duration.

Primary outcome measures

The primary endpoint is the clinical performance of the restorations measured according to the rating system published by Hickel et al. [16].

In the past, USPHS (or Ryge) criteria have been used to evaluate the clinical performance of restorative materials. These criteria were developed as a standardized method to clinically evaluate the quality of an amalgam or resin restoration shortly after placement. The word “quality” means the degree of excellence or degree of conformance to a standard. The rating system is based on an operational approach to quality assessment, which a dentist would use when examining any restoration in the mouth of a new patient. The dentist must decide whether to retain or replace the restoration [17].

This rating system has been in use for over 30 years of clinical investigation. Because the clinical performance of restorative materials has continuously improved, the original Ryge criteria have been modified frequently, which makes it difficult to compare studies on modern restorative materials.

Hickel et al. have offered a new approach to controlled clinical studies of restorative materials. Their publication deals with, among other issues, an adaptation of the established Ryge-criteria of restorative materials [16]. With this rating system, which will be used in this

study, restorations are evaluated scoring for their esthetic, functional and biologic properties.

Secondary outcome measures

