- Have xerostomia caused by medications, Sjögren's syndrome, etc.
- Are individuals with special needs.

Distribution of restorations

Each subject shall have a minimum of one pair and a maximum of two pairs of permanent molar or premolar teeth requiring moderate sized Class II restorations. No tooth shall require more than one restoration. Sufficient subjects will be recruited to ensure 50 pairs of test and control study restorations are placed. Although desirable, the pairs are not required to be precisely matched. For example, for purposes of the study, paired restorations can be placed in teeth #15 and #31 (upper left second molar and lower right second molar).

All teeth and restorations in the study will have occlusal contacts. All restorations, with the exception of disto-occlusal restorations in the most distal molars, will have a proximal contact with the adjacent tooth. No two test restorations of either material will be in occlusal or proximal contact with each other.

Selection of Teeth

In addition to the above criteria, the following will apply in tooth selection:

- The tooth must be vital, as determined by thermal test (Hygenic Endo-Ice, Coltène/Whaledent AG).
- The tooth must be of typical size, appearance and morphology.
- The tooth must share, where appropriate, sound proximal contacts with adjacent teeth.
- The tooth must be free of cracks and other defects and lesions necessitating operative intervention other than the restoration to be undertaken as part of the study.
- Proper isolation must be possible.

MATERIALS

The test material is Filtek™ Bulk Fill Posterior Restorative, a bulk fill, low-shrink, light-cured, radiopaque composite resin restorative indicated for use in direct posterior situations. The control material is Filtek™ Supreme Ultra Universal Restorative, a conventional composite resin. Restorations will be bonded with Scotchbond Universal Adhesive.

Manufacturers' instructions for use will be followed for all restoration placements included in the study. Manufacturers' instructions for use for Filtek™ Supreme Ultra Universal Restorative and Filtek™ Bulk Fill Posterior Restorative, and Scotchbond Universal Adhesive are given in the Investigator's Brochure.

PRE-OPERATIVE PROCEDURES

In the screening visit, written informed consent will be obtained from each subject. Each subject will be allowed to ask questions concerning the evaluation and to consider the answers given before signing the consent form.

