In the event of a restoration being considered to be clinically unsatisfactory, this restoration will be excluded from the study and arrangements made to replace or, if appropriate, repair the defective or failed restoration. The mode of failure of the restoration will be documented (Failed Restoration Form).

The examiners assigned to review the restorations will have been trained in the evaluation system to be used, and will be capable of achieving at least 85% reproducibility in their assessments.

The reviews will take place at one, two, three, and five years \pm 1 month after placement.

Adverse events or adverse device effects

The Investigators are responsible for identifying adverse events, any untoward medical occurrence, that occurs to each subject throughout the study. Adverse events must be documented on the (Serious) Adverse Event Form (Appendix 2). Serious adverse events must be reported to the Sponsor within 24 h. Study subjects who have experienced an adverse event may remain in the study as long as the safety, rights and /or welfare of subjects

are not put at risk and/or the restoration is unaffected concerning its quality and function. Serious adverse events are adverse events that (a) led to a death; (b) led to a serious deterioration in the health of the subject, or (c) led to fetal distress, fetal death or a congenital abnormality or birth defect.

A device-related adverse event is one considered by the investigator to have a reasonable likelihood of being associated with the investigational device and is called an adverse device effect. Adverse device effects must be documented on the Adverse Device Effect Form. Serious adverse device effects must be reported within 24 h to the contact person at **3M ESPE, [contact]**. A serious adverse device effect is an effect that resulted in any of the consequences characteristic of a serious adverse event.

(Near) Incident is any malfunction or deterioration in the characteristics and/or performance of a device, as well as any inadequacy in the labelling or instruction for use, which might lead or might have led to the death of a patient or user or to a serious deterioration in his state of health.

Any incident that led to any hazard for the patient has to be regarded as adverse device effect and documented accordingly. The Investigator reports serious (near) incidents as soon as possible and no later than 24 h to 3M ESPE.

SUBJECT INCENTIVES

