All restorations carried out in this study will be at no cost to the subjects. Subjects will be expected to attend the one-, two-, three-, and five-year follow up visits. Compensation of \$50 will be paid to each subject at baseline and each follow-up visit (total of \$250).

MONITORING

The study will be monitored at appropriate intervals by [name], Scientific Affairs Manager, 3M ESPE Dental Products, [name] [[contact]], or his designee, by means of regular contact to evaluate study data and photographs.

DATABASE MANAGEMENT

Each subject recruited into the study will be given a unique identifying code number and the subject's identity will be kept confidential as far as is practical.

ANALYSIS OF THE RESULTS

The demographic and baseline measurements, and the study data obtained, will be analyzed by means of tables of percentages to summarize the characteristics of the patients and the baseline data. Tables of percentages will be prepared to illustrate the follow-up and retrospective analysis findings. Cross tabulation will be prepared as necessary.

Statistical analyses

Chi-square (χ^2), McNemar and Mann-Whitney-U tests will be applied as appropriate to compare the baseline and follow-up/review findings regarding the two types of restorations.

PROBLEM CASES

In the case of an experimental Filtek™ Bulk Fill Posterior Restorative or Filtek™ Supreme Ultra Universal Restorative composite resin restoration being found to have failed or to be clinically unsatisfactory on review, the investigator will:

- Complete the failed restoration form.
- Make a photographic and silicone impression record of the failed restoration.
- Make arrangements to replace or, if appropriate, repair the restoration.

Replacements of failed restorations will not form part of the study.

In the case of failure of restorations placed using either restorative system, the tooth will be re-restored at no cost to the subject or investigator. The contact person at 3M ESPE ([name], [contact]) should be notified before this treatment is done.

ADVERSE EVENTS

If an adverse event occurs any decision as to whether to prematurely stop the study will be taken jointly by the PI, 3M ESPE, and IRB. Changes to the protocol will be by arrangement between the PI, IRB, and 3M ESPE, and will take the form of a signed amendment.

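### Restorations judged unsatisfactory leave the study and no cumulative failure analysis is specified, so read literally no planned result is a five-year failure rate by material

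*Combined protocol and SAP*

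**What the plan says.** - **Failed restorations.** Follow-up Assessment: "In the event of a restoration being considered to be clinically unsatisfactory, this restoration will be excluded from the study". The same sentence arranges repair or replacement, and the next requires the mode of failure to be put on a Failed Restoration Form. Problem Cases applies the form to a restoration "being found to have failed or to be clinically unsatisfactory on review" and adds that replacements are not part of the study.
- **Analysis.** Analysis of the Results: "Tables of percentages will be prepared to illustrate the follow-up and retrospective analysis findings". The Statistical analyses paragraph applies chi-square, McNemar and Mann-Whitney tests, as appropriate, "to compare the baseline and follow-up/review findings regarding the two types of restorations". Neither gives a denominator, numbers at risk, a cumulative failure proportion or a survival method.
- **Hypothesis.** The two materials are expected to perform similarly "in terms of wear resistance, marginal integrity, durability, and other clinical characteristics". Reviews fall at one, two, three and five years, and Reports to Sponsor requires a report after each.
- **Numbers.** Fifty pairs are to be placed. The stated basis is a guideline: "Fifty restorations available at baseline and 40 at the 18-month follow-up visit are the minimum number". No failure rate, margin or power is given. Under Distribution of restorations, "Each subject shall have a minimum of one pair and a maximum of two pairs" of eligible teeth.

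**The concern.** Whether a restoration leaves depends on the outcome being compared. If one material fails more often in the first three years, more of its restorations have gone before year 5, and those left are the ones that did well. A year-5 table of restorations still in the study can then look similar for both materials when their five-year failure rates are not.

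Durability over five years is a cumulative quantity. The plan collects what is needed to compute it but does not say that anyone will. It also leaves open whether the year-5 denominator is every restoration placed or only those still being scored. Two analysts following the same text could report different year-5 percentages from the same data, and the choice could be made after the failures are known.

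**Working it through.** The plan has no figure to reproduce, because the 50 pairs rest on a guideline minimum. The check is therefore a reading of the analysis text, then an illustration with assumed rates.

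**Reading.** The exclusion sentence removes the restoration, and the analysis paragraphs describe findings at reviews. No sentence returns a removed restoration to a later denominator or adds failures across reviews. On the literal reading, the year-5 comparison is conditional on surviving the year-3 review.

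**Inputs.** From the protocol: 50 restorations per material and reviews at years 1, 2, 3 and 5. Assumed: a constant annual failure rate *a*, no other loss, independent failures.

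**Formulas.** Proportion not yet failed: S(t) = (1 − a)^t.
- Cumulative five-year failure: 1 − S(5).
- Failure shown at year 5 among those still in the study: 1 − S(5)/S(3) = 1 − (1 − a)^2.
- Share of five-year failures absent from that table: (1 − S(3))/(1 − S(5)).

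**Main case, 4% vs 1% a year.**
- Cumulative: 1 − 0.96^5 = 18.46%; 1 − 0.99^5 = 4.90%; difference 13.56 points.
- Year-5 table: 1 − 0.96^2 = 7.84%; 1 − 0.99^2 = 1.99%; difference 5.85 points.
- Absent share, test material: (1 − 0.96^3)/(1 − 0.96^5) = 11.53/18.46 = 62%.
- Expected test failures: 50 × 0.1846 = 9.2 over five years, of which 50 × (0.8847 − 0.8154) = 3.5 are in the year-5 table.

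**Range of rates.**

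| Test vs control, per year | Cumulative at 5 years | Year-5 table, still in study | Test failures absent |
|---|---|---|---|
| 4% vs 1% | 18.5% vs 4.9% (13.6 points) | 7.8% vs 2.0% (5.9) | 62% |
| 3% vs 1% | 14.1% vs 4.9% (9.2) | 5.9% vs 2.0% (3.9) | 62% |
| 2% vs 1% | 9.6% vs 4.9% (4.7) | 4.0% vs 2.0% (2.0) | 61% |

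**Range of timings.** Hold five-year failure at 18.5% vs 4.9% but move the test material's excess. If it falls wholly in year 1 or wholly in years 2 and 3, the year-5 table shows 2.0% vs 2.0% and omits 91% of the test failures. If it falls after year 3, the table shows 16.0% vs 2.0% and omits 16%.

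**Power.** A simulation of 50 independent pairs with no loss compared the chance that at least one of the four reviews is significant at 0.05, unadjusted, with one cumulative year-5 test.

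| Timing of excess | Exact McNemar: any review vs cumulative | Uncorrected chi-square: any review vs cumulative |
|---|---|---|
| Year 1 | 65% vs 44% | 82% vs 60% |
| Years 2–3 | 26% vs 44% (45% by rounding) | 65% vs 60% |
| Constant | 8% vs 44% | 40% vs 60% |
| After year 3 | 54% vs 44% | 75% vs 60% |

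With 20% of pairs lost after year 1, McNemar gives 65.5% vs 32.8%, 12.9% vs 33.1%, 4.2% vs 32.7% and 37.8% vs 32.9%, in the same order. The direction changes with timing and test, and four unadjusted looks against one is not a like-for-like contest.

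**Precision after the fix.** Approximate 95% half-width = 1.96 × √[(p_t(1 − p_t) + p_c(1 − p_c))/50]. This is 12.3 points at 18.5% vs 4.9% and 10.1 points at 9.6% vs 4.9%.

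**The case against.** The strongest reply is that nothing is lost. Scores 4 and 5 belong to the primary rating scale, a failure is scored at the review that finds it and goes on a form, and every review is reported. Because the exclusion shares a sentence with repair or replacement, it can fairly be read as meaning only that scoring stops. Nothing forbids a cumulative table, and the undefined reference to retrospective analysis might cover one.

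Most of this stands, and it rules out some stronger readings:
- A reader might infer that failures are concealed or that durability goes unmeasured. The documents do not support that: an excess in year 1 shows at year 1, and one after year 3 shows at year 5.
- A reader might infer that the plan generally loses power. The figures above do not support that.
- A reader might infer that the relative effect is diluted. In the constant-rate case it is not: 7.84/1.99 = 3.9 at year 5 against 18.46/4.90 = 3.8 cumulatively.
- A reader might infer that the surviving partner of a failed restoration always drops out. That follows only if McNemar compares test with control. The text also allows baseline against review within a material.

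The reply does not supply the missing rule. That a cumulative table is permitted does not make it planned, and the kinder reading of the exclusion is not written down. Cumulative failure could be rebuilt from the four reports if numbers at risk were printed, but the plan does not ask for them.

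**Conclusion.** The point holds as a matter of estimation. On the literal text, comparisons after year 1 are conditional on survival and no planned result is a five-year cumulative failure rate by material, although durability is hypothesised to be similar. At 4% vs 1% a year, the year-5 table would show a 5.9-point difference where the cumulative difference is 13.6 points. At 2% vs 1% it would show 2.0 against 4.7.

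The size rests on assumed rates, no loss to follow-up and the strict reading of the exclusion. If the sponsor meant only that scoring stops and all placed restorations stay in the denominator, these gaps vanish and only the wording needs correcting. The plan should be changed because the text does not settle which reading applies and settling it is cheap.

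**What to change.** 1. **Follow-up Assessment.** Replace the exclusion wording with: *receives no further scoring but is counted as a failure from that review onward*. Care of the tooth is unaffected.
2. **Failure event.** Define it as a restoration for which a Failed Restoration Form is completed, and show repaired and replaced restorations separately as well. Follow-up Assessment excludes unsatisfactory restorations, Problem Cases names failed and unsatisfactory ones, and Table 1 uses the unsatisfactory label for a score of 4 on any single item. Some items, such as patient's view or plaque, can reflect the subject rather than the restoration. These passages must be reconciled so that the trigger for the form is unambiguous.
3. **Analysis of the Results.** Add one life-table of cumulative failure by material at 1, 2, 3 and 5 years with numbers at risk, failures timed at the review that found them and loss to follow-up censored.
4. **Interval.** Report the five-year difference with a 95% interval that respects pairing and subjects and remains valid with few or no failures, for example a paired score-type interval with a subject-level resampling check. Resampling alone is fragile: at 1% a year, 50 control restorations have no failure in five years with probability 0.99^250 = 8%. Resampling by subject is still needed because a subject may contribute two pairs. State in advance which interval is the reported one.
5. **Keep the tests at each review**, since they can be the more sensitive ones for a year-1 or late excess, and label criterion-level results after year 1 as conditional on survival.

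**Cost.** One sentence, one definition, one table and one interval. Failures are already documented, and for losses the protocol says "A record will be maintained of the reasons for the loss of subjects from the study". The failure form is not shown, so the review date may have to come from the Case Report Form. Later failure percentages will look less favourable, and 50 pairs still leave about 10 to 12 points of uncertainty either way.
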